12.5.1. Acceptability Metrics

The primary metric for demonstration of feasibility is the incremental improvement in specificity. An improvement of approximately 5% would be indicative of a successful feasibility study. The percentage of correct downgrades is the next most important metric. Other metrics including sensitivity and NLR will be considered supported evidence.

13. ADMINISTRATIVE CONSIDERATIONS

13.1. Investigators and Study Administrative Structure

Each site will have a designated investigator and one or more study coordinators collectively responsible for the conduct of the study inclusive of referral, screening, enrollment, evaluation, documentation, and subsequent biopsy in accordance with FDA guidelines.

13.2. IRB Committee

The protocol and the informed consent form, and any other institution-specific documents, must have the approval of a properly constituted IRB Committee responsible for approving clinical studies. The signed IRB

Committee approval letter must specify the date of protocol and informed consent form approval and identify the documents approved including the investigator's name, the protocol version, date and title. Any subject materials or advertisements used to recruit subjects should also be reviewed and approved by the IRB Committee.

13.3. Ethical Conduct of the Study

This study will be conducted in accordance with the ethical principles outlined within FDA and GCP regulations as well as local IRB requirements.

13.4. Informed Consent

A signed Informed Consent Form (ICF) must be obtained from the subject prior to performing any study-related procedures. The investigator or investigator's designee will provide background information on the study, including the benefits and risks of all study-related procedures to the subject. The investigator or investigator's designee will also encourage the prospective subject to ask questions about the study and will provide the subject with sufficient opportunity to consider whether or not to participate. After written consent has been documented, previously obtained clinical radiographic data can be used for the study.

Original signed informed consent forms must be filed in the subject records at the site. A copy of the signed consent/assent form should also be provided to the subject.

The ICF for this study will be prepared by the study investigator for conformance with the government and institution's requirements for this class of diagnostic imaging. However, all changes requested by an investigator or an Ethics Committee, even those that may not be considered substantial and/or do not affect the rights, safety or welfare of a subject, must be approved by Seno. If Seno determines that the revisions are substantial and/or affect the rights, safety or welfare of a subject, the ICF must be reviewed and approved by both Seno and the Institutional Review Board before the ICF can be utilized.

13.5. Subject Confidentiality

Confidentiality will be maintained in accordance with FDA and IRB regulations. Subject names must not be revealed to the sponsor or sponsor's representatives. Only the subject identifier (number) will be recorded in the eCRF and if the subject's name appears on any other document, it must be redacted and replaced with the subject identifier before a copy of the document is supplied to the sponsor or sponsor's representatives. Study findings stored on a computer will be stored in accordance with local data protection laws. In the event of inadvertent communication of such information, immediate steps to redact the information from all study files will be implemented, with appropriate documentation in the subject study file.

13.6. Case Report Forms and Study Records

Data will be recorded using an electronic data capture (EDC) system, according to FDA regulations. The database is considered validated when the expected results are the same as the actual results, and the end users verify that the database performs according to the requirements.

The data will include collecting images and videos plus the Laser Optical Movie (LOM) to be sent to the Seno and/or the Central Imaging Core Lab as applicable.

The validation report, design procedures, testing results, source code, and test eCRF cases are filed in the central files. Database maintenance will be provided throughout the study, as well as user support and administration (access and site user rights set-up, removal, etc.)

The MedDRA dictionary will be used to code adverse device effects.

The investigator is responsible for maintaining adequate and accurate medical records from which information will be transferred into the study database.

13.7. Clinical Quality Assurance

The sponsor, or the sponsor's representative, may conduct audits at the investigational sites. Audits may include, but are not limited to, device supply, presence of required documents, the informed consent process, and comparison of eCRFs with source documents (original medical records, images). The investigator agrees to participate with audits conducted at a reasonable time, in a reasonable manner.

13.8. Protocol Amendments

Any amendment to the study protocol must be approved by the sponsor. A protocol amendment may not be implemented until after it has been approved by the IRB, unless immediate implementation of the change is necessary for subject safety. In this case, the protocol change must be documented in an amendment.

Once a protocol amendment has received approval from the sponsor, it will be submitted to the IRB Committee for written approval.

13.9. Protocol Deviations

Protocol deviations may occur in two ways.

1. Deviations from the protocol, contrary to protocol specifications (i.e., deviations from the protocol procedures, eligibility, instructions for use, visit windows, etc.).
2. Deviations affecting the endpoint outcome not previously specified in the protocol (i.e., deviation that had not been previously considered in the protocol or eligibility criteria, but having a clear impact on the primary outcome measure)

The investigator is not allowed to deviate from this protocol except as specified in FDA regulations. The Investigator should not implement any deviation from or changes to the protocol without approval by Seno and prior review and documented approval/favorable opinion from the IRB of a protocol amendment, except where necessary to eliminate immediate hazards to study subjects, or when the changes involve only logistical or administrative aspects of the study (e.g., change in monitors, change of telephone numbers). While every effort should be made to avoid protocol deviations, should a deviation be discovered, Seno must be informed immediately. Any protocol deviation impacting subject safety must be reported to A. [name]. Seno's Medical Director immediately.

Deviations will be documented in the eCRF. Investigators will also adhere to procedures for reporting investigation deviations to their ethics committee in accordance with their specific reporting policies and procedures.

Prior to final database lock, all protocol deviations will be reviewed and categorized as major (i.e., those that affect measurement or interpretation of the primary endpoint or related to safety) or minor (those not affecting

the primary endpoint). The presence of a major deviation will exclude subjects from the Intention to Diagnose (ITD) analysis population.

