7.4. Subject Withdrawal Criteria

Subjects may be discontinued from the study for the following reasons if deemed appropriate by the Sponsor and /or Investigator:

- Subject enters the study in violation of the protocol;
- Subject deviates from the protocol during the study;
- Pregnancy;
- Withdrawal of consent;
- If in the opinion of the investigator it is not in the subject's best interest to continue (reason for withdrawal must be specified); and,
- Termination of the study by the sponsor.

Protocol Deviations will be reviewed by the Sponsor on a routine basis and any deviation that results in the exclusion of the subject from the statistical analyses will be documented in the final clinical study report.

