12.2. Analysis Populations

All analyses will be performed with the intention to diagnose (ITD) study population which consists of all subjects coming in for their scheduled Imaging Visit, having Imago OA data declared evaluable, and having a biopsy of at least one nodule with evaluable cytology/histology results.

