12.5. Analyses

The following outlines the steps to be taken to develop and tune the image creation and colorization algorithm and to develop the guidelines and interpretations rules that will be subsequently applied by three independent readers. The steps will be performed collaboratively by the software engineer and Medical Director, with potential input at earlier stages from the site radiologists.

DEVELOPMENT OF GUIDELINES, INTERPRETATION RULES AND ESTIMATORS

1. Images and data will provide a basis for algorithm finalization, potential instrument improvements, the development of guidelines for interpretation of OA studies of thyroid nodules. Permit Imago OA optimizations with respect to specific parameters (e.g. illumination and detection conditions, laser pulse repetition rate, sound propagation characteristics, etc.). Optimizations may be different for thyroid nodules and for suspicious cervical lymph nodes.
2. Compare *in vivo* opto-acoustic images with those obtained from standard diagnostic thyroid ultrasound, color Doppler imaging (CDI), power Doppler imaging (PDI), strain elastography (SE), or shear wave elastography (SWE).

3. Compare the in vivo opto-acoustic features with those obtained from standard diagnostic thyroid ultrasound color Doppler imaging (CDI), power Doppler imaging (PDI), strain elastography (SE), or shear wave elastography (SWE).
4. Compare findings of conventional imaging modalities and those of opto-acoustic imaging with biopsy results for nodule size, location, type, and stage.
5. Develop Imago-based estimators for thyroid use.

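### Section 13.9 excludes subjects from the only analysis set for deviations identified by their effect on the primary outcome, and nothing masks that classification

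*Combined protocol and SAP*

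**What the plan says.** Section 13.9 (Protocol Deviations) names two kinds of deviation. The first is a departure from something the protocol specifies. The second is a "deviation that had not been previously considered in the protocol or eligibility criteria, but having a clear impact on the primary outcome measure". On timing, the section says "Prior to final database lock, all protocol deviations will be reviewed and categorized as major" or minor. Major means "those that affect measurement or interpretation of the primary endpoint or related to safety". The consequence follows: "The presence of a major deviation will exclude subjects from the Intention to Diagnose (ITD) analysis population".

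Section 12.2 (Analysis Populations) states "All analyses will be performed with the intention to diagnose (ITD) study population". It defines ITD by three conditions: attendance at the imaging visit, evaluable OA data, and a biopsy with an evaluable result for at least one nodule. It does not mention deviations and names no other set.

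On who does what, Section 7.4 says "Protocol Deviations will be reviewed by the Sponsor on a routine basis", and Section 13.9.1 has the sponsor evaluate deviations at monitoring visits. Neither names the person who makes the final major/minor call. Section 5.4 (Blinding) gives site investigators all subject data, including the Imagio images and the pathology report. Section 12.5 describes rule development, in which imaging findings are compared with biopsy results: "The steps will be performed collaboratively by the software engineer and Medical Director".

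Section 7.4 also contains a safeguard: "any deviation that results in the exclusion of the subject from the statistical analyses will be documented in the final clinical study report".

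**The concern.** An exclusion rule is safe when it rests on an act or event that can be recognised without knowing how the test performed. The second deviation type in 13.9 has no such anchor. It is by definition not foreseen, and what identifies it is its effect on the primary outcome. It then falls within the definition of major, so the subject leaves the only set analysed.

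The plan does not require whoever classifies deviations to be unaware of the OA result, the TI-RADS change or the pathology. If those are known, a departure in a nodule that OA got wrong is more likely to be judged endpoint-affecting than the same departure in a nodule that OA got right. Removing the former flatters the device. The study declares success at a specificity gain of about 5% (Sections 7.3 and 12.5.1), and Section 1.4 says its results will shape the pivotal objectives and endpoints.

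**Working it through.** **1. The two definitions of ITD.** Take a subject with evaluable OA data, evaluable pathology and a major deviation. Under 12.2 the subject is in ITD; under 13.9 the subject is out. The sections disagree on the primary analysis set.

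**2. What the plan's own sample-size figure covers.** Section 12.4 goes from 100 evaluable nodules to 110 enrolled for about 10% loss: 100 x 1.10 = 110. (Dividing instead, 100/0.90 = 111.1, or 112 rounded up; 110 x 0.90 = 99.) Section 12.4 attributes the loss to inadequate cytopathology; Sections 3.2 and 4.1 add unacceptable OA images. None of the three mentions major-deviation exclusions.

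**3. How many nodules the 5% mark represents.** Section 12.5 defines specificity as the share of benign nodules with a final TI-RADS of 1 or 2. Let n be the number of benign nodules, b those that OA moves into TI-RADS 1-2 and c those it moves out. Then

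specificity gain = (b - c)/n.

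The documents do not give n. Subtracting the minimum of 20 non-benign nodules in 12.4 (10 papillary, 10 follicular) from 100 evaluable gives n = 80, an assumption. A gain of 5% then needs a net 0.05 x 80 = 4 nodules. Over an assumed range it needs a net 2 at n = 30, 3 at n = 50 and 5 at n = 88.

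**4. Effect of dropping one nodule.** Assume n = 80, b = 4, c = 1.
- All kept: (4 - 1)/80 = 3.75%.
- The one wrong-way nodule dropped: 4/79 = 5.06%.
- One nodule that was simply not downgraded dropped: 3/79 = 3.80%. Reaching 5% this way takes 20 exclusions: 3/60 = 5.0%.

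**5. Other assumed counts.**
- n = 80, b = 6, c = 4: 2/80 = 2.50%; one wrong-way nodule dropped, 3/79 = 3.80%; two dropped, 4/78 = 5.13%.
- n = 80, b = 5, c = 5: 0%; four dropped, 4/76 = 5.26%.

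**6. A stress case.** In 400,000 simulated trials with no true improvement, n = 80 and 5% of benign nodules moved each way on average, the chance of an observed gain of at least 5 points was 10.5% with no exclusions and 27.6% after dropping up to two wrong-way nodules. With 10% moved each way it was 19.0% and 35.2%. Across n = 30 to 88 and both rates, the ranges were 6.3% to 26.7% and 18.3% to 55.9%. This is the unfavourable end, because every exclusion is a wrong-way nodule. The movement rates are assumptions.

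**7. Sensitivity and negative likelihood ratio (NLR).** With 20 non-benign nodules and one missed, sensitivity is 19/20 = 95%; dropping the missed nodule gives 19/19 = 100%. Section 12.5 defines NLR for a dichotomous test as (1 - sensitivity)/specificity. The numerator goes from 0.05 to 0, so NLR falls to 0 whatever the specificity. Dropping a benign false positive raises the denominator and also lowers NLR. Favourable exclusion therefore biases NLR downward.

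**The case against.** The strongest reply is that 13.9 concerns measurement validity. A poor OA result is not itself a deviation, so some departure must first have occurred. A biopsy of the wrong nodule, a labelling mix-up or a device fault can be judged without knowing whether OA was right. Classification precedes final lock, deviations are recorded in the eCRF and reported to the sponsor, and exclusions appear in the study report. This is a feasibility study with no formal test and a mark that is only approximate.

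Much of this stands, and it rules out several stronger readings that a reader might infer.
- That the classifier must look at the outcome: the documents do not say so, and many deviations can be judged without it.
- That the sponsor's team will already have compared OA with biopsy results when deviations are classified: the plan does not time rule development or the three independent reads against that review.
- That subjects can disappear unreported: Section 7.4 says otherwise.
- That one exclusion is enough to reach the mark: this holds only for chosen counts such as 4 against 1, and needs a benign nodule that starts at TI-RADS 1-2. Such nodules may be few, since subjects have suspicious nodules referred for biopsy and 12.4 allows later enrolment to be limited to categories 3 to 5.

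What the reply does not meet is the core point. The text gives no list or criterion that holds classifiers to the measurement-validity reading. OA images, site assessments and pathology can all be available before lock. Disclosure tells the reader who was excluded, but no planned analysis shows what the result would have been with them.

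**Conclusion.** The concern holds as a statement about what the rule permits. Section 13.9 allows exclusions informed by the outcome from the only analysis set, without masking and without an analysis that puts the subjects back. It does not show that such exclusions will occur or are intended. The bias, if it arose, would favour the device: specificity gain and sensitivity up, NLR down.

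The size depends on which nodules leave. On the assumed counts, one wrong-way nodule is worth about 1.3 points (3.75% to 5.06%), and one nodule that was not downgraded about 0.05 points (3.75% to 3.80%). No sensitivity threshold exists, so a change from 95% to 100% would alter supporting evidence only. The benign count, movement counts and movement rates are all assumptions. The conflict between 12.2 and 13.9 depends on none of them.

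**What to change.** - Reconcile 12.2 and 13.9 so that the primary analysis keeps every eligible nodule with evaluable OA and evaluable pathology, except for a short closed list of exclusions written in advance. Align that list with the enrollment failures in 7.5, which already cover ineligibility found after the scan, scans that fail review and unusable biopsy results.
- Delete impact on the primary outcome as a ground for exclusion. Unforeseen deviations can still be recorded and labelled major for reporting.
- Have deviations classified by existing staff masked to OA scores, reader scores and pathology, before reader results are opened, and state this timing in 13.9.
- Report the set without major deviations as a sensitivity analysis beside the primary one.

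The cost is protocol and SAP wording, one masked review of the deviation listing and one extra set of tables. No new data are needed. The downside is that a few nodules with real deviations stay in the primary analysis and add some noise; the sensitivity analysis shows how much they matter.

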13.9.1. Corrective and Preventive Actions

Seno Medical and her representatives will evaluate protocol deviations during monitoring visits. Individual event corrective and preventive actions may be recommended at that time. In addition, deviations occurring across investigational sites will be reviewed by Seno Medical on a periodic basis to determine if more global preventive actions may be required.

13.9.2. Investigator Disqualification Criteria

Seno Medical reserves the right to terminate an investigator/observational site for any of the following reasons:

- Failure to secure subject informed consent including protection of personal data prior to enrollment.
- Failure to report unanticipated adverse device effects within 24 hours of discovery (to Seno Medical) and to the ethics committee within its required reporting time after learning of the event.
- Failure to report serious adverse device effects within 24 hours of discovery.
- Repeated investigational plan deviations.
- Repeated failure to appropriately complete case report forms.
- Failure to enroll an adequate number of subjects.
- Loss of or unaccounted for investigational product inventory.

13.10. Retention of Data

All records, including compact disks of images, must be retained at each clinical site and by Seno or Seno's representatives for a period of two years after the latter of the following two dates: the date the study is closed or terminated or the date of the last approval of a marketing application and records are no longer needed to support a regulatory submission. All study records may be relevant to regulatory inspection.

In the event that the Principal Investigator retires, relocates, or for other reasons withdraws from the responsibility of keeping the study records, custody must be transferred to a person who will accept the responsibility and the sponsor must be notified.

Seno or Seno's representatives should be contacted in advance if there is a desire to discard or relocate any records or if there are any questions regarding record retention.

Seno or Seno's representatives will maintain all records related to this study, according to FDA and IRB regulations.

Required regulatory reports will be submitted per FDA guidelines.

13.11. Statement of Compliance

This clinical investigation will be conducted in compliance with the principles that have their origin in the Declaration of Helsinki, this clinical investigation plan, requirements of the approving ethics committee, FDA and GCP Regulations and other applicable regulatory requirements.

This clinical investigation will not be initiated until approval has been obtained from the IRB committee. Any additional requirements imposed by the IRB committee will be followed. No deviation from the protocol will be implemented without the prior review and approval of the IRB committee except where it may be necessary to eliminate an immediate hazard to a subject. In such case, the deviation will be reported to the IRB committee as soon as possible.

13.12. Financial Disclosure

Investigators will be asked to provide financial disclosure prior to authorization to begin the study as well as after the study is completed. Investigators will also be expected to share any situations which could introduce site-specific bias.

13.13. Publication and Disclosure Policy

The results of the study are the property of Seno Medical Instruments, Inc. All publications (manuscripts, abstracts or other modes of presentation) must be submitted at a time determined by Seno Medical Instruments, Inc. and must be reviewed and approved in writing by Seno Medical Instruments, Inc., in advance of submission. Co-authorship with any Seno Medical Instruments, Inc. personnel will be discussed and mutually agreed upon before submission of a manuscript to a publisher.

APPENDIX A ACR GUIDELINES

Revised 2013 (Resolution 16) *

The American College of Radiology, with more than 30,000 members, is the principal organization of radiologists, radiation oncologists, and clinical medical physicists in the United States. The College is a nonprofit professional society whose primary purposes are to advance the science of radiology, improve radiologic services to the patient, study the socioeconomic aspects of the practice of radiology, and encourage continuing education for radiologists, radiation oncologists, medical physicists, and persons practicing in allied professional fields.

The American College of Radiology will periodically define new practice parameters and technical standards for radiologic practice to help advance the science of radiology and to improve the quality of service to patients throughout the United States. Existing practice parameters and technical standards will be reviewed for revision or renewal, as appropriate, on their fifth anniversary or sooner, if indicated.

Each practice parameter and technical standard, representing a policy statement by the College, has undergone a thorough consensus process in which it has been subjected to extensive review and approval.

The practice parameters and technical standards recognize that the safe and effective use of diagnostic and therapeutic radiology requires specific training, skills, and techniques, as described in each document.

Reproduction or modification of the published practice parameter and technical standard by those entities not providing these services is not authorized.

